### 3.8 Independent Radiology Committee

An IRC will be established to evaluate tumour scans and prior radiation history data of study subjects in a central, blinded and independent fashion. The IRC will be comprised of board-certified radiologists who will evaluate prior radiation history to validate the identification of target lesions, as well as determine radiographic response and progression after screening. All IRC assessments will be performed by batch (any additional details will be found in the IRC charter).

Additional imaging results may be requested by the Sponsor for IRC review.

Details regarding IRC member qualification, training, methods, procedures, and other issues relevant to committee operations will be described in the IRC Charter.

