g Microscopic urine examination to be performed at baseline and after that only at the discretion of the Investigator (results are not to be collected in the eCRF except in case of clinically abnormal findings, which are to be reported as an AE). Urine chemistry (24-hour urine protein or UPCR) may be performed at any scheduled or unscheduled visit at the discretion of the Investigator and based on results of routine urinalysis or as clinically indicated.

CONFIDENTIAL

FINAL PROTOCOL (INCLUDING AMENDMENT #4): 23 FEBRUARY 2022PAGE 49/228

h Follow-up for radiographic progression, tumour assessment should be performed until radiographic progression confirmed by the Investigator only for subjects who have discontinued cabozantinib treatment before radiographic disease progression and who have not withdrawn consent.

 Cabozantinib will be self-administered at home until study treatment is discontinued.

j Information on new or worsening AEs will be collected from date of the signed informed consent until the end of study treatment, at each study visit, by telephone call or by spontaneous report by the subject. Any AEs and SAEs that are ongoing 30 days after the date of the last cabozantinib dose are to be followed until resolution or until the Investigator considers the event is stable or irreversible (see [Section 8.1.3](#)).

k During the follow-up period, any SAEs that occur more than 30 days after the date of the last cabozantinib dose, assessed as related to study treatment or study procedures will also be collected and followed until resolution or stability according to the Investigator.

l Information on prior and concomitant medication will be collected up to 30 days before baseline until 30 days after the date of the last cabozantinib dose.

m *The FACIT and all related works are owned and copyrighted by, and the intellectual property of [name]. Permission for use of the FCSI-DRS questionnaire is obtained by contacting [name] at [[contact]](mailto:[contact]).*

Based on an average treatment duration of 8 months and 12 visits, the total volume of blood drawn for all evaluations throughout this study will be approximately 144 mL for each subject (12 mL of blood per visit, this volume may depend on the laboratory used, treatment duration and number of visits).

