### 5.2.3 *Procedures After Study Treatment*

Subjects who discontinue study treatment with cabozantinib will be invited to enter the Post-treatment Follow-up period. All necessary assessments performed after treatment are indicated in [Table 2](#).

For subjects who have discontinued cabozantinib treatment before radiographic disease progression and who have not withdrawn consent, tumour assessment should be performed until radiographic progression confirmed by the Investigator.

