#### *11.4.3.4 Secondary Efficacy Endpoint Analyses*

The ORR according to Investigator's assessment (cohort A and cohort B) and by independent central review (cohort B) will be presented with their associated 2-sided 95% CIs using Clopper-Pearson exact method. Discordance in ORR assessed by independent central review and by Investigator will be described.

DCR estimates will be presented in statistical tables with associated 2-sided 95% CIs.

Time-to-event endpoints (TTR, DOR, PFS and OS) will be analysed using the Kaplan-Meier method. The results will be presented for each Cohort A and B both in summary tables and graphically in Kaplan-Meier plots. Kaplan-Meier methodology will be used to characterise the

distribution of endpoints. Median durations and associated 2-sided 95% CIs will be provided. Event rates at timepoints from either first dose of study treatment or first documented response will also be estimated with associated 2-sided 95% CIs.

General censoring rules for the analysis of PFS are described below:

- Subjects who receive non-protocol anti-cancer therapy (NPACT) after start of cabozantinib and before experiencing an event will be right censored at the date of the last tumour assessment prior to the date of initiation of subsequent therapy;
- Subjects who have not experienced an event (and are not otherwise censored) at the time of data cut-off will be right censored on the date of their last tumour assessment;
- Subjects who miss two or more scheduled tumour assessments followed by an event will be right censored on the date of their most-recent tumour assessment prior to the missing assessments.

Additional supportive analyses of PFS will be defined in the SAP using alternative event definitions and censoring schemes to account for partial or completely missing assessments, address bias due to tumour assessment timing, evaluate the impact of potentially informative censoring, and to address potential discrepancies between the documentation of progression per the Investigator and per the independent central review.

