| 12-lead ECG | ≤15 Days prior to baseline | X (prior to first dose) ^f | | X | | Every 12 weeks | X | |
| Haematology and blood biochemistry | ≤15 Days prior to baseline | X (prior to first dose) ^f | X | X | X | Every 4 weeks | X | |
| Coagulation assessments | ≤15 Days prior to baseline | X (prior to first dose) ^f | X | X | X | Every 4 weeks | | |
| Urinalysis, microscopic urine examination and urine chemistry (including UPCR) ^g | ≤15 Days prior to baseline | X (prior to first dose) ^f | X | X | X | Every 4 weeks | X | |
| Pregnancy test (female subjects only, if applicable) | ≤7 days prior to baseline | X (prior to first dose) ^f | Urinary and/or pregnancy blood tests are mandatory at every visit | | | | X | |
| Thyroid function test (FT4, TSH) | ≤15 days prior to baseline | X (prior to first dose) ^f | Every 4 weeks | | | | X | |
| Chest/Abdomen/Pelvis (C/A/P) CT/MRI | ≤28 days prior to baseline | X ^f | Every 12 weeks (±10 days) while on protocol treatment beginning at Week 12 (i.e. Week 12, Week 24, Week 36, etc) until the end of study and additionally if clinically indicated | | | | | X ^h |
| Brain CT/MRI and Bone scintigraphy Scan (only if indicative of metastases) | ≤28 days prior to baseline | Only if indicative of brain and/or bone metastases at screening or if signs or symptoms suggestive of metastases develop | | | | | | X ^h (only if indicative of metastases) |

CONFIDENTIAL

SAP Final: Version 6.0: 17 August 2023

| | Pre-treatment Period | Treatment Period | | | | | | Post-treatment Follow-up Period ^d |
|--|-----------------------------------|---|---|------------------------|------------------------|---------------------------------|--|--|
| Assessment | Screening | Baseline ^a | Week 2 | Week 4 | Week 8 | Every 4 weeks | End of Study Treatment Visit ^b or Early Study Withdrawal Visit ^c | Follow-Up |
| | Visit 1 | Visit 2 | Visit 3 | Visit 4 | Visit 5 | Visit 6 to Visit X | 30 days after the last dose of treatment | Every 12 weeks |
| | Before first cabozantinib intake | Day 1 | Day 15 (± 2 Days) | Day 29 (± 2 Days) | Day 57 (± 2 Days) | Day 85 to Day X (± 5 Days) | (+15 Days) | (± 15 Days) |
| Cabozantinib intake ⁱ | | All subjects will be treated with oral cabozantinib 60 mg once daily (q.d.). In case of treatment-emergent toxicity, the Investigator may decide to reduce the dose to 40 mg or 20 mg | | | | | | |
| Dispense/return of oral study drug and compliance accounting | | X | | X | X | X | X | |

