Concordance in Overall Response Rate and BOR assessed by independent central review and by Investigator will be described using shift tables for each cohort separately (Tables 14.2.4.3 and 14.2.4.4). The concordance will be presented for the subjects with assessments in both populations i.e. from both IRC and investigator assessments.

General censoring rules for the analysis of PFS are described in [Appendix 1 \(4\)](#).

Additional supportive analyses of PFS below will be performed using alternative event definitions and censoring schemes to account for partial or completely missing assessments, address bias due to tumour assessment timing, evaluate the impact of potentially informative censoring, and to address potential discrepancies between the

SAP Final: Version 6.0: 17 August 2023

documentation of progression per the Investigator and per the independent central review. This is applicable for PFS only. These additional supportive analyses will be performed on the Efficacy population only.

- The primary PFS analyses described above will be repeated with the same general censoring rules, except that the progression or death will be considered a PFS event regardless of when it occurs during the study i.e. the event will be considered a PFS event even if the subjects missed two or more scheduled tumour assessment prior this event and/or even if the subjects received NPACT prior the event (Table 14.2.2.4, Figure 14.2.2.5, Table 14.2.5.5 and Figure 14.2.5.6);
- The primary PFS analyses described above will be repeated with the same general censoring rules, except that non-radiological disease progression will also be considered a PFS event (Table 14.2.2.6, Figure 14.2.2.7, Table 14.2.5.7 and Figure 14.2.5.8).
- The primary PFS analyses described above will be repeated with the same general censoring rules, with additional censoring at last tumour assessment prior to treatment discontinuation for subjects who discontinued study treatment due to reasons other than PD or death (Table 14.2.2.8, Figure 14.2.2.9, Table 14.2.5.9 and Figure 14.2.5.10).

3.2.2 *Safety*

All safety data will be included in the subject data listings. Analyses and summary tables will be based upon the safety population as defined in Section 2.2 and will be presented in each cohort separately and overall.

3.2.2.1 *Adverse events*

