In case of non-censoring and a partial progression/death date, missing day will be imputed by the first day of the month. This will be the most conservative approach considering that the earliest date for progression/date. It will be imputed by the date of initial response in case the date of initial response is later than the imputed date.

In case of censoring and a partial last tumour assessment date, missing day will be imputed by the first day of the month. It will be imputed by the date of initial response in case the initial response is later than the imputed date. The censoring may occur earlier than the exact date.

(4) Time-to-Progression for Progression-Free Survival (PFS) analysis

PFS is defined as the time from start of study treatment to either disease progression (as determined by independent central review per RECIST 1.1) or death due to any cause, whichever occurs first. For subjects who are not known to have died or progressed at the time of data cut-off for PFS analysis, the PFS will be censored at the last tumour assessment and considering the censoring rules defined in the table below.

| Event | Decision | Date of event or censoring |
|---|--------------|---|
| Progressive disease with no more than one missing scheduled tumor assessment before the event and without NPACT before the event. | Not censored | Date of first progressive disease |
| Death with no more than one missing scheduled tumor assessment before the event and without NPACT before the event. | Not censored | Date of death |
| PD or death with two or more missing scheduled tumor assessments before the event | Censored | Date of the last tumor assessment prior to the missing assessment. |
| PD or death with NPACT after the start of cabozantinib and before the event | Censored | Date of the last tumor assessment prior to the date of initiation of NPACT. |
| No event (no PD, no death) with at least one radiological | Censored | Date of last radiological assessment |

SAP Final: Version 6.0: 17 August 2023

| | | |
|---|----------|-----------------------------------|
| assessment after the initiation of study treatment. | | |
| No event (no PD, no death) without any radiological assessment after the initiation of study treatment. | Censored | Date of first cabozantinib intake |

PFS will be calculated as:

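### When a subject off cabozantinib has investigator-called progression that the IRC does not call, IRC-assessed PFS and DOR are censored at the last scan, and no planned supportive PFS analysis tests the effect

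*Protocol*

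**What the plan says.** **Scanning.** On treatment, scans are due every 12 weeks from Week 12, "until the end of study and additionally if clinically indicated" (SAP Table 2). Off treatment, Protocol 5.2.3 states that "tumour assessment should be performed until radiographic progression confirmed by the Investigator". Footnote h of Protocol Table 2 (repeated in the SAP) applies this "only for subjects who have discontinued cabozantinib treatment before radiographic disease progression and who have not withdrawn consent".

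**Reading.** Protocol 11.4.3.2 defines PFS and DOR by IRC progression or death, with investigator versions as further secondary endpoints. Under Protocol 3.8, "All IRC assessments will be performed by batch".

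**Censoring.** In SAP Appendix 1 (3) and (4), a subject with neither IRC progression nor death is censored at the "Date of last radiological assessment". A death counts only if no more than one scheduled scan was missed and no non-protocol anti-cancer therapy (NPACT) came first.

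**Stated aim.** Protocol 11.4.3.4 and SAP 3.2.1.2 give as one purpose of the supportive PFS analyses "to address potential discrepancies between the documentation of progression per the Investigator and per the independent central review".

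**The concern.** A subject who stops cabozantinib because the investigator sees radiographic progression has no further scheduled scan. One who stopped earlier for another reason loses scans once the investigator calls progression. The protocol describes no real-time IRC confirmation. If the later batch read disagrees, there is no further image on which the IRC could call progression, and the IRC analysis censors the subject just when the site judged the disease to be growing.

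Kaplan-Meier estimation assumes that censored subjects have the same future risk as those still followed. That is doubtful here. If investigators tend to call progression a scan or two before the IRC would, the IRC estimates of PFS and DOR come out too long. The plan says its supportive analyses will deal with reader disagreement, so a reader of the report would expect to see this effect bounded.

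**Working it through.** **1. The plan's own figures.** The documents give no event count, power or reader-discordance rate for PFS or DOR, so there is no stated figure on this point to reproduce. The one design figure concerns ORR: 68 evaluable subjects, 10% against 23%. It reproduces (at least 13 responders, exact one-sided alpha 0.0163, power 0.816; 68/0.93 = 73.1, rounded up to 74) and does not bear on this point.

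**2. Who is affected.**
- On drug after investigator progression (allowed by Protocol 5.2.2): scans continue. Not affected.
- Stops drug at investigator progression: outside footnote h, so no further scheduled scan. Affected if the IRC has not called progression.
- Stopped drug earlier, investigator progression later: scans end at that call. Affected on the same condition.

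**3. What each supportive PFS analysis in SAP 3.2.1.2 does for an affected subject.**
- The first counts progression or death despite missed scans or NPACT. It can recover a later death, but not a progression that the IRC never saw.
- The second keeps the general rules, "except that non-radiological disease progression will also be considered a PFS event". Investigator radiographic progression is outside it.
- The third adds censoring for those who stopped for reasons other than progression or death. A subject who stopped for progression is unchanged.

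Each is run separately on IRC and on investigator data. None carries investigator radiographic progression into the IRC analysis. The concordance tables (14.2.4.3 and 14.2.4.4) cover best overall response and ORR only. Investigator PFS (Table 14.2.5.1) and the joint plot (Figure 14.2.5.4) show two curves without isolating this censoring.

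**4. Illustrative size.** Kaplan-Meier simulation, 200,000 subjects per scenario, with 12-week scans and the Appendix 1 (4) rules. From the documents, as borrowed assumptions: a latent IRC progression median of 7.4 months and an OS median of 21.4 months (the METEOR figures in Protocol 1.2.1.1), both taken as exponential and independent. Assumed without support in the documents: investigator progression one or two scans before IRC progression in 10% to 40% of subjects; 0% to 60% of these treated and scanned beyond it; NPACT in 70% of those who stop; cut-off at 12 to 30 months.

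The table gives 12-month PFS for a selection of scenarios. Overstatement is the planned-rules value minus the value if scanning ran to IRC progression.

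| Early calls | Treated beyond | Scans end without IRC progression (of 74) | Planned rules | First supportive analysis | Scanned to IRC progression | Earliest of either reader | Overstatement (points) |
|---|---|---|---|---|---|---|---|
| 10% | 60% | 2.1% (1.6) | 0.247 | 0.248 | 0.242 | 0.234 | 0.5 |
| 10% | 0% | 5.2% (3.8) | 0.254 | 0.255 | 0.239 | 0.232 | 1.5 |
| 20% | 30% | 7.1% (5.3) | 0.260 | 0.262 | 0.240 | 0.225 | 2.0 |
| 30% | 0% | 15.6% (11.5) | 0.288 | 0.290 | 0.239 | 0.216 | 4.9 |
| 40% | 60% | 8.2% (6.1) | 0.264 | 0.265 | 0.240 | 0.210 | 2.4 |
| 40% | 0% | 20.7% (15.3) | 0.308 | 0.308 | 0.240 | 0.210 | 6.8 |

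The overstatement rises with early calls and falls as more subjects are scanned beyond investigator progression. The first supportive analysis shifts the planned result by at most about 0.2 points. Taking the earliest progression by either reader goes below the scanned-to-IRC value, so it bounds from the other side. That column counts early calls in subjects still being scanned as well, so it is at least as low as the analysis proposed here; the two coincide when nobody is treated beyond progression.

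**The case against.** The best counter-argument is that the plan already limits the problem. Protocol 7.3.1 says that investigator progression is not in itself a reason to end scanning or treatment, asks investigators to hold back the call until findings are unequivocal, and sends every scan to the IRC. Appendix 5 continues follow-up of equivocal lesions. These rules target the calls most likely to be discordant. Some deaths still count as events. Investigator PFS, the supportive analyses rerun on investigator data and Figure 14.2.5.4 let a reader compare the two sources. Protocol 11.3 plans no significance test for secondary efficacy endpoints. The timing of the batches is left to the IRC charter, which is not among these documents.

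Much of this stands, and it rules out two broader readings. A reader might infer that scanning stops at investigator progression for everyone; it does not, because subjects kept on drug are still scanned. A reader might also infer that reader discrepancy is nowhere shown, or that investigator PFS is no help because it re-dates every event. The joint plot does describe the discrepancy, and where both readers call progression at the same scan the date is the same.

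The narrower gap remains. Off drug, 5.2.3 and footnote h end the required scans, and the general sentence in 7.3.1 sets no schedule that would restore them; those passages should be reconciled. Two curves side by side do not show how far the IRC curve depends on this censoring.

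**Conclusion.** The point holds for subjects off cabozantinib at or before investigator-called radiographic progression that the IRC has not called. Their censoring is plausibly informative and would lengthen IRC-assessed PFS and DOR where investigator calls precede IRC progression. The stated aim of addressing reader discrepancy is not met by the three analyses listed for IRC PFS.

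The size is unknown. The range of about 0.5 to 7 percentage points at 12 months, with roughly 2 to 15 of 74 subjects affected, rests on assumed rates of discordance, treatment beyond progression and NPACT. It also builds in the direction, by assuming that discordant calls are early ones. Calls unrelated to later IRC progression would not produce this bias.

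Two stronger readings are tempting. With a fraction d of investigator progressions not called by the IRC, a reader might infer that the median is inflated by 1/(1-d), so that a true 8 months becomes 8/0.9 = 8.9, 8/0.8 = 10.0 or 8/0.7 = 11.4 months at d = 10%, 20% or 30%. That treats every discordant call as a true IRC event at that scan, which by construction it was not, so it does not estimate bias in IRC PFS. A reader might also take the lack of a supportive DOR analysis as a broken commitment. It is not: SAP 3.2.1.2 confines the supportive set to PFS.

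This is a worthwhile, inexpensive improvement to secondary endpoints.

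**What to change.** Add to SAP 3.2.1.2 a fourth supportive analysis of IRC-assessed PFS: a subject with investigator radiographic progression, no IRC progression and no later IRC-read scan counts as an event on the investigator's progression date, regardless of later NPACT. Present it beside the main IRC result as a conservative (lower) bound, not as a corrected estimate. Report the number of such subjects by cohort, and add an IRC/investigator concordance table for progression status and date. The same analysis for IRC-assessed DOR would be a useful addition.

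The cost is SAP wording and a few extra tables from data already collected, with no added scans or subjects. The supportive median will probably be shorter than the main one.

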#### 5.2.3.1 *Post-treatment Follow-up Period*

During the Post-treatment Follow-up period, subjects will be contacted every 12 weeks ( $\pm 15$  days), starting after the End of Study Treatment visit, to assess survival status and record the receipt of subsequent anti-cancer therapy. During the follow-up period, any SAEs that occur more than 30 days after the date of the last cabozantinib dose, assessed as related to study treatment or study procedures will also be collected and followed until resolution or stability according to the Investigator. These assessments will be continued until the subject expires or until the end of the study (18 months after the last subject included in the study received the first cabozantinib dose, [Section 5.6](#)), whichever occurs first. Every effort will be made to collect these protocol-specific evaluations unless consent to participate in the study is withdrawn. All AEs will be documented and/or followed as described in [Section 8.1.3](#) and [Section 8.1.4](#).

At each contact, the Investigator (or designee) will determine if the subject has died, and if so, record the date and cause of death as best as can be determined. All efforts must be undertaken by the investigational sites to determine the date of death (or the date the subject was last known to be alive at the time of a data cut-off). This may include, but not necessarily be limited to, telephone calls, registered letters, and reviews of local obituaries and government death records. If a subject is lost to follow-up, multiple attempts to contact study subject or designee must be documented in the subject records.

Every effort will be made to perform protocol-specific evaluations unless consent to participate in the study is withdrawn and the subject no longer allows data collection.

